# 1 INTRODUCTION AND OBJECTIVES OF ANALYSIS

## 1.1 Introduction

This statistical analysis plan (SAP) is designed to outline the methods to be used in the analysis of study data to answer the study objective(s). Details regarding the management of all data and statistical methodology, including an explanation of the analyses of exploratory endpoints and imputation of missing data, are included in the SAP, which will be finalized prior to the protocol specified [REDACTED]. The statistical analyses and summary tabulations described in this SAP will provide the basis for the results sections of the clinical study report (CSR) for this trial.

## 1.2 Objectives

**Table 1: STAR-0215 Objectives & Endpoints**

Primary Objective	Primary Endpoints

 
To assess the safety and tolerability of SC administration of single and multiple doses of STAR-0215 in participants with Type I or Type II HAE
 
	
 
Incidence of adverse events
 
Changes in vital signs, ECG findings, physical examination findings, and clinical laboratory evaluations
 

Secondary Objectives	Secondary Endpoints

 
To assess the clinical activity of SC administration of single and multiple doses of STAR-0215 in participants with Type I or Type II HAE
 
To characterize the PK of SC administration of single and multiple doses of STAR-0215 in participants with Type I or Type II HAE
 
	
 
Change from baseline in monthly HAE attack rate
 
Incidence of HAE attack severity (mild, moderate, and severe)
 
Duration of HAE attack (shorter than 12 hours, 12 to 24 hours, 24 to 48 hours, and longer than 48 hours)
 
The number of HAE attacks requiring on-demand- therapy
 
Time to first HAE attack after first and last dosing
 
Concentration of STAR-0215 and the derived PK parameters
 

 
• To characterize the PD of SC administration of single and multiple doses of STAR-0215 in participants with Type I or Type II HAE
 
• To assess the immunogenicity of SC administration of single and multiple doses of STAR-0215 in participants with Type I or Type II HAE
 
	
 
• Change in plasma kallikrein activity
 
• Formation of anti-drug (STAR-0215) antibodies
 

Exploratory Objectives	Exploratory Endpoints

 
• To evaluate the impact of STAR-0215 on [REDACTED] of STAR-0215
 
• To conduct an exploratory assessment of the effect of STAR-0215 on [REDACTED] in participants with Type I or Type II HAE
 
	
 
• Changes from baseline in [REDACTED] STAR-0215
 
• Changes from baseline in the [REDACTED]
 

## 2 STUDY DESIGN

### 2.1 Introduction

STAR-0215-201 is a multicenter, single- and multiple-dose study to assess the safety, tolerability, clinical activity, PK, PD, and immunogenicity of STAR-0215 in participants with Type I or Type II HAE. STAR-0215 is a humanized IgG1 kappa light mAb, designed to be a highly potent and specific inhibitor of plasma kallikrein, with a YTE-modified Fc domain to enable delayed clearance and prolonged time in circulation. The study design is a standard approach to the evaluation of the safety and tolerability of an investigational product.

Properly consented participants will undergo screening assessments according to the inclusion and exclusion criteria (Protocol Section 5.1 and Section 5.2, respectively) and immediately enter the Run-In period. During the Run-In period, HAE attack information will be collected to determine if a participant meets the eligibility requirement of experiencing at least 2 HAE attacks during this time period and to establish a baseline prior to STAR-0215 administration. If a participant has an HAE attack during the Run-In period before Day 1 (first dose of STAR-0215), all signs and symptoms of the HAE attack must be resolved before dosing. A washout period for on-demand treatment is not required. The Run-In period may be extended after consultation with the Medical Monitor. In Cohorts 2 and 3, if a participant has an HAE attack immediately before the second dose (Day 84 and Day 28, respectively), signs and symptoms of the HAE attack should be improving per participant report prior to STAR-0215 administration; a washout period for on-demand treatment is not required before the second dose is administered.

In Cohort 1, each participant who has completed the Run-In period and is eligible for STAR-0215 administration will receive 1 dose of STAR-0215 on Day 1. When Cohort 1 has completed dosing, the [Safety Review Committee \(SRC\)](#) will review the cohort's cumulative safety data from the Screening/Run-In period through 21 days after dosing. Progression to Cohort 2 dosing will occur if there are no concerning safety signals. (Protocol Section 4.2)

In Cohort 2, each eligible participant will receive 2 doses of STAR-0215, the first on Day 1 and the second on Day 84. [REDACTED]

In Cohort 3, each eligible participant will receive 2 doses of STAR-0215, the first on Day 1 and the second on Day 28.

Provided no safety concerns are noted from a cumulative review of safety data from this study and the ongoing FIH study (STAR-0215-101), [REDACTED] and [REDACTED] may be explored in [REDACTED]

STAR-0215 will be administered SC into the abdomen. There are planned to be 4 participants in Cohort 1, 6 participants in Cohort 2, and 6 participants in Cohort 3. Based on the accumulated safety information and enrollment as continually monitored by the SRC [REDACTED] (Protocol Section 9.12), up to 6 additional participants may be added to Cohort 2 and/or Cohort 3 (maximum of 12 participants each in Cohorts 2 and 3) [REDACTED]

████████████████████ The dose regimens and dose levels for each cohort are in Table 2. There is no placebo group in this study. An overview of the study design is provided in Table 3.

[figure not shown]
As detailed in the [Schedules of Assessments](#), study assessments will be performed in all cohorts through 6 months after the last dose of STAR-0215 (Day 168 in Cohort 1, Day 251 in Cohort 2, and Day 195 in Cohort 3). At this time, participants who are willing and eligible to consent can begin participation in the long-term open label extension study (STAR-0215-202). For participants who do not enroll in the long-term open label extension study, safety monitoring will be performed through ██████ months after the last dose of STAR-0215 in all cohorts (Day ██████ in Cohort 1, Day ██████ in Cohort 2, and Day ██████ in Cohort 3) through regular contacts and scheduled site visit. Visits subsequent to STAR-0215 administration are scheduled with respect to the actual day of STAR-0215 dosing for consistency and precision in post-dose sample collection. Safety assessments (including AEs, vital signs, ECGs, physical examinations, clinical laboratory evaluations, and pregnancy testing), and efficacy, PK, PD, immunogenicity, biomarker, and ████████████████████ may be conducted at scheduled site visits.

**Table 2: STAR-0215 Dose Regimens**

Cohort	Dose 1		Dose 2		# Participants
	STAR-0215 Dose Level (mg)	Dosing Day	STAR-0215 Dose Level (mg)	Dosing Day	
1	450	1	NA	NA	4
2	600	1	300	84	6; up to 12
3	600	1	600	28	6; up to 12

Abbreviations: NA = not applicable.

**Table 3: Overview of Study Design**

\*Participants may opt to participate in the long-term open label extension trial STAR-0215-202

**Notes:** When Cohort 1 has completed dosing, the Safety Review Committee will review the cohort's cumulative safety data from the Screening/Run-In period through 21 days after dosing. Progression to Cohort 2 dosing will

occur if there are no concerning safety signals. [REDACTED]

## 2.2 Treatment Assignment

This study is not randomized.

All eligible participants will receive STAR-0215. In Cohort 1, participants will receive a single dose of STAR-0215. In Cohorts 2 and 3, participants will receive 2 doses of STAR-0215. There is no placebo group in this study. Dose regimen and dose level information for each cohort is provided in Table 2.

## 2.3 Safety Review Committee and Stopping Rules

The SRC will be composed of a clinician with expertise in HAE, a medical monitor, and representatives from the Sponsor. The SRC will be responsible for making recommendations related to study progression.

The SRC will meet when Cohort 1 has completed dosing and all study visits through 21 days after dosing. The SRC will review the cohort's cumulative safety data, including AEs, results of vital sign assessments, clinical laboratory assessments, and ECG assessments. Cohort 2 will not be dosed until the appropriate data from Cohort 1 have been reviewed by the SRC. There will be ongoing oversight by the SRC, as there may be ad hoc meetings of the SRC upon the emergence of an unexpected safety signal at any time during the study. In the event of emergent safety concerns posing substantial risk to participants, the SRC will consult with the Protocol Stopping Rules.

**Table 4: Stopping Rules for Study STAR 0215-201**

Adverse Event Criteria	Action
At least 2 participants in a dose cohort experience similar SAEs or At least 2 participants in a dose cohort experience similar Grade 2 treatment-related AEs	The SRC will make a recommendation as to continuation, including potentially modifying the starting dose of the subsequent cohort.
Any 1 participant in a dose cohort experiences a Grade 3 or greater treatment-related AE	Dosing for the participant and the remainder of the cohort will be halted until a review of the event by the SRC is completed and the SRC has made a recommendation.

Adverse Event Criteria	Action
Any occurrence of a treatment-related SAE	May result in suspension of any further dosing in the study by the Medical Monitor until the SRC has evaluated the event and determined the next appropriate course of action.

Abbreviations: AE = adverse event; SRC = Safety Review Committee; SAE = serious adverse event.

## 2.4 Blinding

This is an open-label study.

## 2.5 [REDACTED]

In preparation for future clinical development of STAR-0215 and subsequent study planning, [REDACTED] of data in accumulating cohorts are planned (Table 5). The [REDACTED] [REDACTED] was planned to occur after the [REDACTED] in [REDACTED] reaches the [REDACTED] visit. However, enrollment into the study was faster than anticipated and the [REDACTED] [REDACTED] in [REDACTED] have the [REDACTED] visit [REDACTED] [REDACTED] participants have data up to 90 days post first dose therefore it was decided that the [REDACTED] will include the [REDACTED] visit for these [REDACTED] and all other available data from [REDACTED]. In addition, for the same reasons, the [REDACTED] will occur after the [REDACTED] in [REDACTED] reaches [REDACTED] of STAR-0215 (the [REDACTED] visit) and will include all available data from [REDACTED]. At each [REDACTED] the Sponsor will review the accumulated safety, efficacy, PK, PD, and immunogenicity data. If no safety concerns are noted following [REDACTED], efficacy, PK, PD, and immunogenicity results may inform the decision to add additional participants to Cohorts 2 or 3 (up to a total of 12 in each) and/or [REDACTED] exploring [REDACTED] and [REDACTED].

A [REDACTED] will occur when the first 16 participants dosed complete the study. Separate analyses of the 'Initial 16 Participants' and cumulative data for all participants dosed at the time of data cut-off will be performed on the accumulated safety, efficacy, PK, PD, and immunogenicity data.

The IA will summarize safety, efficacy, PK, PD and immunogenicity (ADA) by cohort; as described in section 6 and per Table 5. Listings and figures will also be provided.

Additional ad hoc or unplanned administrative analyses may be performed to monitor safety, PK, PD, ADA and/or efficacy.

**Table 5:** [REDACTED]

[REDACTED]	[REDACTED]	[REDACTED]	[REDACTED]
[REDACTED]	[REDACTED] in [REDACTED] reaches the [REDACTED] [REDACTED] visit	All available cumulative safety, PK, PD, immunogenicity, and efficacy data through the [REDACTED] visit in [REDACTED] and the [REDACTED] visit in [REDACTED]	
 
• Potential addition of up to 6 participants to Cohort 2 (maximum of 12 participants total)
 
• [REDACTED]
 
• [REDACTED]
 

[REDACTED]	[REDACTED] in [REDACTED] reaches [REDACTED] after [REDACTED] [REDACTED] (the [REDACTED] visit)	All available cumulative safety, PK, PD, immunogenicity, and efficacy data through the [REDACTED] visit in [REDACTED] the [REDACTED] visit in [REDACTED] and the [REDACTED] visit in [REDACTED]	
 
• Potential addition of up to 6 participants to Cohort 2 and/or Cohort 3 (maximum of 12 participants total in Cohorts 2 and 3)
 
• [REDACTED]
 
• [REDACTED]
 
• Inform Sponsor's decision-making regarding [REDACTED]
 

[REDACTED]	[REDACTED] dosed completes study	All available cumulative safety, PK, PD, immunogenicity, and efficacy data for all participants enrolled	Inform Sponsor's decision-making regarding [REDACTED]

Abbreviations: PD = pharmacodynamics; PK = pharmacokinetics.

### 3 STUDY ENDPOINTS

#### 3.1 Primary Endpoints

- Incidence of adverse events (AEs)
- Change from Baseline in vital signs, electrocardiogram (ECG) findings, physical examination findings, and clinical laboratory evaluations

#### 3.2 Secondary Endpoints - Efficacy

- Change from baseline in monthly HAE attack rate, overall and per month.
  - 50%, 70%, and 90% overall reduction of HAE attacks
  - Investigator assessed HAE Attack definition is given in Protocol section 7.12.1:

To be considered an HAE attack, the Investigator must confirm that the event has signs or symptoms consistent with an HAE attack that meet at least 1 of the following criteria: Peripheral angioedema, Abdominal angioedema, or Laryngeal angioedema.

Prodromal symptoms or participant-reported use of on-demand HAE attack treatment alone are not sufficient to define an event as an HAE attack.

Each HAE attack must be unique. To be distinct from the previous attack, the new symptoms must occur at least 24 hours after resolution of the prior attack's symptoms.

The HAE attack resolution is defined as the participant no longer having symptoms of the HAE attack. The HAE attack severity will be graded by the Investigator.
- Proportion of participants who are HAE attack free
- Incidence of at least one HAE attack by maximum severity (mild, moderate, and severe), including participants without any attacks.
- Duration of HAE attack (shorter than 12 hours, 12 to 24 hours, 24 to 48 hours, and longer than 48 hours).
- The number of HAE attacks requiring on-demand therapy.
- Time to first HAE attack after first and last dosing, censored to End of Study visit.
- HAE attack free days, from treatment start until End of Study.

#### 3.3 Secondary Endpoints - Pharmacokinetic, Pharmacodynamics (PD) and immunogenicity

- Concentration of STAR-0215 and the derived PK parameters
  - Maximum drug concentration (Cmax)

- Time of Cmax (Tmax)
- Area under the curve (AUC) after a defined duration or at steady state
- Circulating half-life ( $t_{1/2}$ )
- Apparent clearance (CL/F)
- Volume of distribution (V/F)
- Change in plasma kallikrein activity (PD)
- Formation of anti-drug (STAR-0215) antibodies

### 3.4 Exploratory Endpoints

- Changes from baseline in the [REDACTED]

For the evaluation of the questionnaire, the total score is/will be measured based on [REDACTED], and the domains are/will be evaluated separately. The [REDACTED]. The [REDACTED] corresponded with the average of items found in one domain. The [REDACTED]

- Changes from baseline in [REDACTED] of STAR-0215

## 4 ANALYSIS SETS

### 4.1 Analysis Set Definitions

For all analysis sets, participants will be analyzed according to the assigned dose cohort.

#### 4.1.1 Safety Analysis Set

The Safety Analysis Set is defined as all participants who received any amount of STAR-0215. This analysis set will be the primary analysis set for all safety, biomarker and immunogenicity (ADA) endpoints.

#### 4.1.2 Efficacy Analysis Set

The Efficacy Analysis Set is defined as all participants who received any amount of STAR-0215 and have 1 post-baseline assessment of HAE attack (conducted at each treatment period visit). This analysis set will be the primary analysis set for all clinical activity endpoints. Additionally, this analysis set will have no important protocol deviations that could affect the evaluation of clinical activity parameters.

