6.3.1. Prohibited Medications

Use of the following treatments will not be permitted during the study:

- Long-term prophylaxis for HAE (use of C1-INH for long-term prophylaxis, kallikrein inhibitors, attenuated androgens, or anti-fibrinolytics). See [Section 7.15](#) for additional details pertaining to the use of certain permitted prophylaxis medications for participants who do not participate in the long-term open label extension study
- ACE inhibitors
- Estrogen-containing medications with systemic absorption (such as hormonal contraceptives or HRT). Topical estrogens applied externally or intravaginally are allowed, provided the Investigator and Medical Monitor agree that the systemic absorption is minimal and unlikely to have health impacts to the participant.
- Androgens (e.g. stanozolol, danazol, oxandrolone, methyltestosterone, testosterone)
- Any investigational drug or device
- Any other mAb
- Vaccine doses within the 7 days before or after STAR-0215 administration

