9.3.2. Efficacy Analysis Set

The Efficacy Analysis Set is defined as all participants who received any amount of STAR-0215 and have 1 post baseline assessment. This analysis set will be the primary analysis set for all efficacy endpoints. Additionally, this analysis set will have no major protocol deviations that could affect the evaluation of efficacy parameters.

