### 4.2 Protocol Deviations

Protocol Deviations will be classified as Important or Non-Important. Important Protocol Deviations may lead to removal of participants' data from efficacy, PK or PD analysis. The list of protocol deviations will be reviewed by the Sponsor, the principal investigator and the study statistician. Determination of whether important deviations have an impact on any of efficacy,

PK or PD assessments, will be determined prior to any formal analysis. A report of Protocol Deviations (excel or csv format) will include important /non-important distinctions, category, description, population impact (each of efficacy, PK or PD), in addition to dates and other relevant variables.

The number (%) of participants with at least one protocol deviation and the number (%) of participants with at least one important protocol deviation will be summarized. For the important protocol deviations, the number (%) of participants in each deviation category will be presented.

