## 6.4 Efficacy Evaluation

All analyses of HAE attack data will be presented using the Efficacy Analysis Set. Both Run-In and Post-Treatment period will be displayed where applicable.

All HAE attacks that occurred on study will be listed for both Run-In and Treatment periods.

A summary of Run-In period HAE attack assessments will include Location of HAE attacks (Abdominal, Laryngeal, Peripheral); the baseline (Run-In period) values of: HAE attack rate, HAE attacks by worst severity (none/attack-free, mild, moderate, and severe), duration of each participants longest HAE attack, number and proportion of HAE attacks requiring on-demand therapy, and HAE Attack Free Days. This summary will be repeated for the first dose period.

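### The only efficacy set excludes participants for unlisted, discretionary deviations in an open-label trial, and no all-dosed efficacy estimate is planned

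*SAP*

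**What the plan says.** SAP 4.1.2 starts from everyone given any study drug who has a post-baseline attack assessment. It then adds that "this analysis set will have no important protocol deviations that could affect the evaluation of clinical activity parameters". Its role is stated plainly: "This analysis set will be the primary analysis set for all clinical activity endpoints". Protocol 9.3.2 has the same structure with a different adjective: "this analysis set will have no major protocol deviations that could affect the evaluation of efficacy parameters".

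SAP 6.4 says "All analyses of HAE attack data will be presented using the Efficacy Analysis Set". The Safety Analysis Set, which keeps every dosed participant, serves safety, biomarker and ADA endpoints (SAP 4.1.1). No efficacy summary is assigned to it, and no efficacy sensitivity analysis on a different set is named.

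SAP 4.2 governs the exclusions. On their effect it says: "Important Protocol Deviations may lead to removal of participants' data from efficacy, PK or PD analysis". On who reviews them it says: "The list of protocol deviations will be reviewed by the Sponsor, the principal investigator and the study statistician". Whether a deviation affects efficacy, PK or PD "will be determined prior to any formal analysis". Neither document lists the deviations that count as *important* or *major*.

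Several other provisions bear on this:
- The study is open-label (SAP 2.4).
- Attack information is collected weekly and confirmed by investigators (Protocol 7.12).
- The sponsor reviews accumulated efficacy data at each interim (Protocol 9.12), and SAP 2.5 allows ad hoc looks at efficacy as well.
- Long-term HAE prophylaxis is prohibited during the study (Protocol 6.3.1). Some agents become permitted only after the 6-month visit (Protocol 7.15).
- SAP 6.2.6 scores participants who discontinue treatment as non-responders on binary endpoints.

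**The concern.** An exclusion made after outcomes are known, under no written list of criteria, can depend on those outcomes. Here the people who review deviations either confirm the attacks or can see them. Fixing the decision before formal analysis limits the freedom to choose but does not blind it. For any deviation that arises or is reclassified after the first interim, the sponsor has already reviewed efficacy. The SAP modification history records that attack analyses were done with IA1 before version 2.0.

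A plausible route runs through prophylaxis. A participant whose attacks return during the treatment period may start a prohibited long-term agent. That breaches Protocol 6.3.1 and could clearly affect the efficacy evaluation, so it is a natural candidate for exclusion, yet it is also a treatment failure. If that participant is removed, the failure leaves the attack-rate change, the responder and attack-free proportions and the Kaplan-Meier estimates together. These results may inform the decision to enlarge Cohorts 2 and 3.

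**Working it through.** **Cohort sizes.** Protocol 4.3 and SAP Table 2 give 4, then 6 up to 12, then 6 up to 12. The plan's maximum reproduces: 4 + 12 + 12 = 28; the initial total is 4 + 6 + 6 = 16. No alpha, power or effect size is given, so no sample-size formula applies.

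**Weight of one exclusion.** 1/4 = 25.0%; 1/6 = 16.7%; 1/12 = 8.3%.

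**Effect on a responder proportion.** The documents give no outcome data, so the outcomes below are assumed. With x responders among n, removing one non-responder raises the proportion by x/(n−1) − x/n = x/[n(n−1)]. For x = 4, n = 6 this is 4/30 = 13.3 points: 4/6 = 66.7% becomes 4/5 = 80.0%.

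With one failure per cohort (x = n−1) the gain is 1/n. Exact Clopper-Pearson limits are the 2.5% point of Beta(x, n−x+1) and the 97.5% point of Beta(x+1, n−x), with the upper limit set to 100% when all respond:

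| n | Failure kept | Failure excluded |
|---|---|---|
| 4 | 3/4 = 75.0% (19.4 to 99.4) | 3/3 = 100% (29.2 to 100) |
| 6 | 5/6 = 83.3% (35.9 to 99.6) | 5/5 = 100% (47.8 to 100) |
| 12 | 11/12 = 91.7% (61.5 to 99.8) | 11/11 = 100% (71.5 to 100) |

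**Effect on mean percent change, n = 6.** Assume five responders at −100, −100, −95, −90 and −85, which sum to −470. The interval is mean ± t(0.975, n−1) × SD/√n.
- Failure excluded: −470/5 = −94.0% (−102.1 to −85.9).
- Failure kept at −30%: −500/6 = −83.3% (−111.4 to −55.2).
- Failure kept at 0%: −470/6 = −78.3% (−119.1 to −37.6).
- Failure kept at +50%: −420/6 = −70.0% (−132.0 to −8.0).

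Exclusion enlarges the apparent mean reduction by 10.7 to 24.0 points and narrows the interval sharply.

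**Does another rule catch this case?** The non-responder rule in SAP 6.2.6 is triggered by stopping treatment. The last dose is on Day 1, 84 or 28, and the HAE treatment period ends on Day 168, 251 or 195 (SAP Table 2 and 5.2). The remaining time is 168 − 1 = 251 − 84 = 195 − 28 = 167 days in every cohort. In those 167 days no scheduled dose remains to be discontinued. SAP 5.4 keeps data up to withdrawal but does not restore someone excluded from the set.

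**Is simple retention enough?** SAP 6.4.1 computes the rate as attacks divided by days, times 30.4375. Suppose a participant has *a* attacks by day *d*, starts prophylaxis, and has none to day *D*. The uncensored rate is (a/D) × 30.4375, against (a/d) × 30.4375 up to the start of prophylaxis. The first understates the second by the factor d/D. Keeping such a participant without a handling rule would therefore also flatter the drug.

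**The case against.** The case on the other side has real weight.

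The plan is transparent. SAP 6.4 lists every on-study attack, and SAP 6.3.1 gives set counts and listed reasons for exclusion. SAP 4.2 requires a deviation report showing population impact. With 4 to 12 participants per cohort, a reader of those outputs could largely rebuild an all-dosed responder count by hand. That stands, but a listing is not a planned estimate. A reader might infer that excluded failures would be invisible, and the documents do not support that.

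The decision is not left to the sponsor and investigator alone. The study statistician also reviews deviations, and impact is settled before formal analysis, which can be read as before each one. The interim timing is redacted, so how many decisions would follow a look at efficacy cannot be established. What survives is that outcomes are known throughout an open-label trial.

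The prophylaxis route is an inference. No text classes prophylaxis use as important. Breakthrough attacks are not deviations and on-demand treatment is permitted (Protocol 6.3.2), so ordinary failures stay in the set. The route is confined to the HAE treatment period, because certain agents are allowed afterwards. Other exclusions, such as too few run-in attacks or recent lanadelumab, would not be post-dose failures.

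A reader might also infer that exclusion always favours the drug. It does not: compared with keeping a prophylaxis user uncensored, the direction is not fixed.

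**Conclusion.** The concern holds as a design weakness. The plan permits outcome-related exclusion from every HAE attack summary, its criteria are unlisted and discretionary, and it schedules no all-dosed estimate to set beside the result.

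One exclusion carries 25%, 17% or 8% of a cohort of 4, 6 or 12. The shifts in proportions and means rest on assumed outcomes and show sensitivity only; the documents give no deviation or response rates. The conclusion also assumes that a deviation such as prohibited prophylaxis would be judged important, which no rule requires or prevents.

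The stakes are bounded. Efficacy is secondary and descriptive, with no hypothesis testing planned for it, and the primary safety endpoints use all dosed participants. A reader might infer that failures have been or will be removed. Nothing in the documents shows that. The point is that the plan should not leave the possibility open when closing it is cheap.

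**What to change.** 1. Redefine the primary Efficacy Analysis Set as all participants given any STAR-0215 who have at least one post-dose HAE attack assessment, with no deviation exclusions.
2. Keep the deviation-free set as a labelled sensitivity analysis, and list its qualifying deviations in advance.
3. For participants who start prohibited prophylaxis within the HAE treatment period, count attacks and exposure only up to that date. Censor time to first attack there if they are still attack-free. Score them as non-responder and not attack-free on the binary endpoints. This concerns analysis only and does not touch clinical management.
4. Use one term in both documents, since Protocol 9.3.2 says *major* and the SAP says *important*, and record the change in SAP section 7.

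The cost is more than SAP wording. Protocol 9.3.2 carries the same exclusion, so this needs an aligned protocol or a documented departure from it. The efficacy tables must be rerun, and comparability with the attack analyses already done at IA1 needs a note. Results may be slightly less favourable. Cutting follow-up at a start date prompted by attacks is itself informative, so the affected participants should be identified in the tables. If nobody would have been excluded and nobody starts prohibited prophylaxis, the results are unchanged.
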